2.4 Statistical model

For outcome (1) and (3), we specify the difference in means in the intervention year using the below specification:

$$Y_{ikt} = \alpha + \beta(ECM_i \times Post_t) + \gamma_1 ECM_i + \gamma_2 Post_t + P_i + \tau_t + \pi_k + (\epsilon_i + \eta_k + \zeta_t)$$

Here, Y_{ikt} is the outcome of patient i , with ECM provider k , at time t . ECM_i is an indicator that the patient is selected into the ECM treatment and $Post_t$ is an indicator that the ECM treatment period has started. Therefore β is the difference-in-difference coefficient of interest. P_i are a vector of patient-level controls, such as prior health care seeking, risk status, or health effects (in various models). τ_t are year fixed effects and π_k are provider controls or fixed effects. Standard errors are clustered with provider-year random effects indicated as $\eta_k + \zeta_t$.

For outcome (2), we specify the difference in means in the intervention year using the below specification:

$$Y_{kt} = \alpha + \beta(ECM_k \times Post_t) + \gamma_1 ECM_k + \gamma_2 Post_t + \tau_t + \pi_k + (\eta_k + \zeta_t)$$

Here, Y_{kt} is the outcome provider k , at time t . ECM_i is an indicator that the provider is selected into the ECM treatment and $Post_t$ is an indicator that the ECM treatment period has started. Therefore β is the difference-in-difference coefficient of interest. τ_t are year fixed effects and π_k are provider controls or fixed effects. Standard errors are clustered with provider-year random effects indicated as $\eta_k + \zeta_t$.

Funding statement

This project received funding from the Georgetown University McCourt School of Public Policy Massive Data Institute, the World Bank's Research Support Board, and the World Bank Strategic Impact Evaluation Fund.

Ethics

This study was approved by Harvard Longwood IRB protocol IRB20-114.

References

1. World Health Organization. Noncommunicable diseases: Progress monitor 2020. (2020).
2. World Bank. The state of health care integration in Estonia (2015).

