2. METHOD AND DESIGN

2.1 ECM IE Design Overview

This study incorporates a two stage randomization, first at the clinic level and second at the patient level.

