2.2 Clinic randomization

EHIF identified 421 clinics (786 providers) who were eligible for the ECM program. The study team then excluded clinics which had participated in the pilot study, those not currently operational, as well as clinics with five or more practicing providers. From the remaining 546 clinics, we conducted a stratified sampling via coarsened exact matching with two quality of care measurement indicators – the practice’s Quality Bonus Scheme (QBS) score and a management score given to each clinic³. We grouped all the clinics into blocks of similar performance based on the QBS and management score. From each performance block, we randomly selected one-fourth of the clinics into ECM program.

This sampling resulted in 144 providers randomly selected into ECM and 402 providers in the control group. All providers in randomly selected clinics were enrolled in ECM. After the clinic randomization and after providers were invited to join the ECM program, 47 providers have refused or dropped out. The most common reasons given were lack of time, or other logistical issues, or in some cases health problems with several providers themselves. Since these providers dropped out of the program before the patient classification began, their patient population is excluded from randomization into the program..

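### Outcome (2) compares providers assigned by whole clinic within blocks, but its model has no clinic or block term, and the number of clinics randomised is not stated

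*Combined protocol and SAP*

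**What the plan says.** **Assignment.** The ECM IE Design Overview (2.1) states: "This study incorporates a two stage randomization, first at the clinic level and second at the patient level". Clinic randomization (2.2) adds the detail: "We grouped all the clinics into blocks of similar performance based on the QBS and management score", then "From each performance block, we randomly selected one-fourth of the clinics into ECM program", and "All providers in randomly selected clinics were enrolled in ECM". The exclusions at this step cover pilot clinics, clinics not operating, "as well as clinics with five or more practicing providers". Clinics in the draw therefore had one to four providers.

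**Analysis.** Outcomes (2.3) aggregates domain 2 by provider and makes it secondary. In the Statistical model section (2.4), the treatment variable for this outcome "is an indicator that the provider is selected into the ECM treatment". The model contains ECM × Post, both main effects, year effects, π_k (provider controls or fixed effects, with the choice left open) and the errors η_k + ζ_t. On precision it says only: "Standard errors are clustered with provider-year random effects indicated as" η_k + ζ_t. It names no clinic term, no clustering by clinic and no block term.

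**Counts.** Section 2.2 opens with "EHIF identified 421 clinics (786 providers) who were eligible for the ECM program". After exclusions it reports 546 clinics remaining, and then splits the sample into 144 ECM and 402 control providers, of whom 47 in the ECM group later refused or dropped out. The abstract describes 97 physicians as a random selection out of 786.

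**The concern.** Providers in the same clinic receive the same assignment and share management; the management score exists only per clinic (Provider Sample, 2.4.1). If their QBS compliance changes together over time, 546 providers carry less information than 546 independent units. Provider-level standard errors are then too small and the test of outcome (2) rejects too often.

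Omitting the blocks can act the other way. They were built partly on QBS scores, and outcome (2) is QBS compliance. If blocks explain part of the change, a model without them can overstate the standard error.

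A reader cannot judge which effect dominates. That needs the number of clinics, their sizes and the within-clinic correlation (ICC), and the plan gives none of these. The mislabelled 546 hides the gap, since it looks like a cluster count and is not one. The abstract's wording hides a further fact: the 97 are those left after a loss following selection, not the random draw itself.

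**Working it through.** **1. Reproducing the counts**
- 144 + 402 = 546, so 546 counts providers. It cannot count clinics, because only 421 existed before exclusions.
- 144 − 47 = 97, the abstract's figure. The random draw was 144/546 = 26.4% of providers, close to one-fourth when whole clinics are drawn. It was not 97/786 = 12.3%.
- Loss after selection: 47/144 = 32.6%.
- No number of clinics randomised, in total or per arm, can be recovered from the text.

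**2. Limits on the number of clinics**
With at most four providers per clinic, 546 providers need at least 546/4 = 136.5, so 137 clinics. Some of the 421 were excluded, so at most 420 remain.

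**3. Effect of omitting clinic, with no block effect**
The documents give no ICC, no clinic sizes and no alpha. Assumed: ICC of the provider-level change 0.05–0.5, two-sided 5% test, all 546 providers analysed.

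Formulas, with m the clinic size:
- w = Σm²/546 (provider-weighted clinic size)
- DEFF = 1 + (w − 1) × ICC
- SE ratio (true/modelled) = √DEFF
- type I error = 2 × (1 − Φ(1.96/√DEFF))

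The 421 count is the pre-exclusion figure; 350 is an assumption.

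| Clinics | Size mix | w | SE ratio, type I at ICC 0.05 | SE ratio, type I at ICC 0.5 |
|---|---|---|---|---|
| 421 | 296 solo + 125 pairs | 796/546 = 1.46 | 1.011, 5.3% | 1.109, 7.7% |
| 421 | 379 solo + 1 of three + 41 of four | 1044/546 = 1.91 | 1.023, 5.5% | 1.207, 10.4% |
| 350 | 154 solo + 196 pairs | 938/546 = 1.72 | 1.018, 5.4% | 1.166, 9.3% |
| 350 | 284 solo + 1 pair + 65 of four | 1328/546 = 2.43 | 1.035, 5.8% | 1.310, 13.5% |

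Worked line (last row, ICC 0.5): DEFF = 1 + 1.43 × 0.5 = 1.716; √1.716 = 1.310; 1.96/1.310 = 1.496; type I error = 13.5%.

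At the extreme of about 137 clinics, nearly all of four (w ≈ 4), the SE ratio is 1.07–1.58 and type I error 6.8–21.5%.

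**4. Adding blocks**
Simulation with 10,000 runs per case and one-fourth of clinics assigned within 16 blocks (assumed). Cases: 421 clinics (solo + pairs) and 350 clinics (solo + fours), ICC 0.05 and 0.5, blocks explaining 0 or 20% (assumed) of the variance in change.

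| Quantity | Range over cases |
|---|---|
| True SE/modelled SE, block share 0 | 1.00–1.32 |
| True SE/modelled SE, block share 20% | 0.93–1.25 |
| Type I error, planned model | 3.6–13.8% |
| Type I error, clustered by clinic, no block terms | 2.8–5.9% |
| Type I error, clustered by clinic, with block terms | 5.1–6.6% |
| Interval width relative to plan, clustered with block terms | 0.90–1.24 |

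The planned model can therefore err in either direction, and the correction brings the error rate close to nominal.

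**The case against.** **Provider effects already deal with part of this.** If π_k is taken as provider fixed effects, all stable clinic and block differences drop out, and for a solo clinic provider and clinic coincide. That is correct, and it narrows the point to correlated changes. It does not remove it: β measures change, fixed effects do not absorb clinic-level shocks to change, and the plan leaves open whether π_k is fixed effects at all.

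**The numbers rest on assumptions.** They do. The 421 case is not attainable after exclusions, and 350 clinics, 16 blocks and a 20% block share come from no document. The ranges are illustrations only. The one statement on clinic size, that roughly 70% of providers work solo (2.4.1), would give an SE ratio of about 1.01–1.20 if applied to the 546. But it does not fit the clinic count. About 382 solo clinics (0.70 × 546) plus the other 164 providers in fours (41 clinics) make 423, more than the 421 before exclusions.

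**Block terms mainly buy precision.** With a nearly equal fraction drawn per block, leaving them out seldom invalidates the test, and clustering alone gave 2.8–5.9%. Clinic clustering is the more important part of the remedy. Block terms still match the stratified assignment, and clustering without them can be conservative.

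**Weight.** Outcome (2) is secondary, and section 2.2 reports the 144 and the 47 openly, so the abstract wording is a minor matter. Both points stand and limit the severity.

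**Conclusion.** The concern holds. The outcome (2) model does not reflect assignment by clinic within blocks, and the plan gives an impossible clinic count in place of the number of clusters. These statements, and the correction to the abstract, rest on the text and simple sums and need no assumption.

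The statistical consequence is uncertain in size and, once blocks are considered, in direction. It is small if most clinics are solo or the ICC is low, and material if many clinics have three or four providers whose changes move together. All the illustrative figures assume that the 546 providers are analysed as selected. The treatment indicator points that way, but the plan does not say whether the 47 are kept for outcome (2).

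The primary outcomes in domains 1 and 3 are analysed on patients randomised within provider, so the clustering point does not reach them. This should be fixed before analysis, but it does not threaten the main comparison.

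**What to change.** - **Statistical model, outcome (2):** cluster standard errors by clinic, or add a clinic-level random effect on the change. Include performance-block × Post terms to match the stratified assignment.
- **Clinic randomization:** relabel the 546 as providers. State the number of clinics randomised, in total and per arm, with their sizes.
- **Abstract:** say that 144 providers were selected through clinic randomisation from 546, and that 97 took part after 47 (32.6%) refused or dropped out.

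The cost is one clustering option and block terms in the code, plus wording. No new data are needed: the sampling dataset links providers to clinics (2.4.1), and the study team built the blocks itself. Intervals for outcome (2) may widen or narrow; in the illustrative simulation they were 0.90–1.24 times the planned width. Fixing this before analysis also keeps the choice from looking data-driven.
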